Study design of the pilot RCT: To evaluate the efficacy of a translated EE intervention for endometriosis patients, we conducted a RCT of parallel design with an intervention group (EE intervention) (n=29) and a wait list control group (n=27) from August 2021 to July 2022. Participants randomized to the intervention participated in six EE modules on alternate Saturday mornings. They could receive (or continue receiving) standard gynecological care (hormonal, analgesics, or surgeries) and psychological therapy as needed. Participants randomized to the wait-list control condition were invited to participate in an online seminar about endometriosis and could also receive standard of care for endometriosis and mental health. After providing informed consent, all subjects completed a set of validated surveys at baseline and end of the intervention to assess QoL, perceived stress, anxiety, depression, and pain symptoms, and provided saliva samples. Individuals in the intervention group were followed up 3-months after the study ended to assess possible longterm effects of the intervention. Participants in the control group completed the same questionnaires and provided the saliva samples during house visits that took place within one week before and one week after the timeline of the intervention. Clinical and socio-demographic data, as well as pain catastrophizing scores were obtained with the Endometriosis Phenome Project (EPHect) questionnaire [42]. Participants in the intervention group used WhatsApp chats to continue their communications between meetings. Data regarding treatments and doctor's visits during the study were obtained from all participants with a clinical history questionnaire administered twice during the study period.

*Study surveys*: Participants in the EE condition completed the following surveys at baseline and end of the intervention, and at 3 months after the intervention was completed. Individuals in the control group completed the same questionnaires only at baseline and end of the study period:

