(5) Anxiety (General Anxiety Disorder-7 (GAD-7): This self-administered questionnaire measures anxiety symptomatology through seven items which are scored from 0 to 3. The cut points of 5, 10, and 15 represent mild, moderate, and severe, respectively [48]. Patients reporting moderate-severe scores in GAD-7 were provided with a referral for psychological services.

(6) Patient Health Questionnaire-8 (PHQ-8): This self-administered questionnaire measures depression symptomatology through eight items which are scored from zero to three. Scores of 5, 10, 15, and 20 represent cut points for mild, moderate, moderately severe, and severe, respectively. [49]. Patients reporting moderate-severe scores in PHQ-8 were provided with a referral for psychological services.

(7) Pain catastrophizing scale (PCS): This scale is part of the EPhect-Q Questionnaire that was completed at baseline. The PCS evaluates three dimensions of catastrophizing: helplessness, rumination, and magnification [50]. The scale has a total score of 52 with items scored from 0 ('not at all') to 4 ('all the time') [51]. A PCS score higher than 30 is considered clinically significant and identifies those with a higher risk of chronicity and disability due to pain [52].

**Saliva sampling and cortisol ELISA:** Saliva samples for cortisol were collected at baseline, end of the intervention, and at the 3-month follow up for the experimental group. Saliva samples (approximately 1-3 mL) were obtained by passive drool into pre-labeled 15 mL tubes. These samples were obtained at the same time of the day (between 8:00-9:00am and at noon, before and after the intervention) to account for circadian variations in cortisol levels. For the control group, samples were collected one week before the start of the intervention and one week after during house visits. Control individuals were asked to collect saliva at the same time as the intervention group, on the same day, and store them at 4°C until collection during visits by the research team. Saliva samples were stored short-term on wet ice during transport to the research laboratory where they were processed and stored at -80°C until analysis. Once in the lab, the saliva samples

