were spun down to clear buccal cells, and aliquots stored at -80°C until analysis by ELISA. Cortisol analysis was done using the High Sensitivity Salivary Cortisol Enzyme Immunoassay kit (Salimetrics, State College, PA, cat #130025), validated for the quantitative measurement of salivary cortisol, following the manufacturer's protocol. All samples were assayed undiluted in duplicate on the same assay plate. Cortisol concentrations were calculated based on standard curve, averaged, and reported in mg/dL.

**Statistical analysis:** The pilot trial's acceptability and feasibility were determined by rates of Recruitment, Enrollment, Adherence, Survey completion and Module evaluations.Equivalence of baseline characteristics, as well as between-group differences in clinical-demographics variables and study outcomes were assessed using descriptive and univariate statistics, including T-test or Mann-Whitney test for continuous variables (depending on normality of distribution, as assessed by Shapiro-Wilk test), and Chi-square or Fisher's exact test for categorical variables. Between group differences, as well as changes in the intervention group (from baseline) were evaluated for % improvement. Outcomes were evaluated using repeated two-way analysis of variance and assessed differences in intragroup (baseline vs. end of intervention) and intergroup (intervention vs. control). If findings were significant, we used a Tukey post-hoc test. Clinically meaningful changes in pain were considered when there was a change of three or more points (substantial difference), two to three points in the NRS (moderate difference) or 1 point (minimal difference) [43, 53]. A p value of 0.05 or less was considered statistically significant.

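### Does the unclear account of control-arm saliva collection threaten the cortisol comparison enough to change the plan?

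*Combined protocol and SAP*

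**What the plan says.** The combined document describes control saliva in three places.

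- **Study design of the pilot RCT:** controls "provided the saliva samples during house visits that took place within one week before and one week after the timeline of the intervention".
- **Saliva sampling and cortisol ELISA, first statement:** "For the control group, samples were collected one week before the start of the intervention and one week after during house visits".
- **Same section, next sentence:** "Control individuals were asked to collect saliva at the same time as the intervention group, on the same day", with the instruction to "store them at 4°C until collection during visits by the research team".

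For the intervention arm, the saliva section says only that "Saliva samples for cortisol were collected at baseline, end of the intervention" and at the 3-month follow-up. It gives clock times of 8:00–9:00 am and noon, but no place, calendar day or holding step. The modules are placed by the statement that participants "participated in six EE modules on alternate Saturday mornings".

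The Statistical analysis section does not mention cortisol by name. It says "Equivalence of baseline characteristics, as well as between-group differences in clinical-demographics variables and study outcomes were assessed using descriptive and univariate statistics", and adds a two-way repeated ANOVA with intragroup and intergroup comparisons. It does not say which ANOVA term decides.

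**The concern.** Read quickly, the saliva section seems to contradict itself: control samples are taken at house visits a week outside the programme, and also on the same day as the intervention arm. Only controls are told to refrigerate samples at home, with no time limit. If day, setting or storage differed systematically between arms and this moved measured cortisol, a between-group difference could appear with no effect of the intervention. Tests at a single visit and the ANOVA group effect would be exposed, and the plan does not make group-by-time the cortisol result. The stake is a false cortisol finding in either direction.

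**Working it through.** **Step 1. Can the passages be reconciled?** The saliva section itself uses the word collection for pick-up by the research team. Apply that sense to the house visits:

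| Sample | House visit | Same-day sampling | Compatible? |
|---|---|---|---|
| End | up to 7 days after the programme | day of the last module (assumed) | Yes: held at 4°C for 0–7 days, then picked up |
| Baseline, intervention saliva taken on or before the visit | up to 7 days before the start | on or before the visit | Yes |
| Baseline, intervention saliva taken at module 1 | up to 7 days before the start | module 1 | No: an undescribed pick-up would be needed |

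Only the last row conflicts, and it needs a baseline date that the document does not give. The same-day phrase may also mean only that the morning and noon samples share a day.

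**Step 2. Timing.** Six alternate Saturdays without a break span (6 − 1) × 14 = 70 days. House visits are then 70 to 70 + 7 + 7 = 84 days apart. The inclusion criteria speak of a 3-month commitment. Taking that as 13 weeks (91 days, an assumption) gives 91–105 days. On either count the gap between control visits exceeds the programme by at most 14 days. The document does not link a difference of that size to cortisol.

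**Step 3. What would an offset do?** The document gives no cortisol error rate, SD or stability figure, so there is nothing to reproduce and what follows is hypothetical.

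Inputs: n = 29 and 27 (Study design); two-sided α = 0.05 (level from Statistical analysis, sidedness assumed); one normally distributed value per visit; no true effect; arm offset d in SD units; correlation r between visits. Both d and r are assumed.

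With c = √(29 × 27 / 56) = 3.739 and 54 degrees of freedom, the noncentrality parameters are:

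- single-time test: c·d
- ANOVA group effect: c·d / √((1 + r)/2)
- group-by-time, constant offset: 0
- group-by-time, offset at the end visit only: c·d / √(2(1 − r))

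False-positive rates (r = 0.5, with the range over r = 0.3–0.7 in brackets):

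| d | Single-time | Group effect | Group-by-time, constant offset | Group-by-time, end-only offset |
|---|---|---|---|---|
| 0 | 5% | 5% | 5% | 5% |
| 0.1 | 7% | 7% | 5% | 7% |
| 0.25 | 15% | 19% (17–21) | 5% | 15% (12–22) |
| 0.5 | 45% | 56% (51–62) | 5% | 45% (34–66) |

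A simulation of 20,000 trials at d = 0.5 and r = 0.5 gave 45%, 57% and 5% for the first three tests.

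**Step 4. Would naming group-by-time help?** It removes a constant offset completely. For an end-only offset, the last noncentrality parameter exceeds c·d as soon as √(2(1 − r)) < 1, that is, r > 0.5. The preferred test then does worse than the single-time test. The handling in Step 1 could vary by visit (0–7 days of cold storage at the end, and none or an unknown time at baseline), so a constant offset cannot be taken for granted.

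The choice also costs precision. The difference detectable with 80% power is 0.763 × √(2(1 − r)) = 0.76 SD for change scores at r = 0.5, against 0.763 × √(1 − r²) = 0.66 SD for ANCOVA. ANCOVA is not in the plan, and it would retain d(1 − r) of a constant offset.

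**The case for a change.** The best case for acting is that the remedy is cheap and the plan's own safeguards are weak. The planned baseline comparison, if applied to cortisol, would miss a constant offset of 0.25 SD in 85% of trials and one of 0.5 SD in 55%. At 0.5 SD and r = 0.5, a non-significant baseline test would be followed by a significant end test in 30% of such trials. Group-by-time is immune to a constant offset, and the plan never singles it out.

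The description is indeed incomplete, and a clean baseline test would not prove equal handling. The rest is weaker. These rates are what any two-group test at this sample size gives once a shift is assumed, and nothing in the document suggests that home sampling, another weekday or a cold hold produces one. The plan also works against an offset. Clock times are matched, controls are told to sample on the same day, and samples are reported as assayed in duplicate on the same plate. The plate statement, if it means that the arms shared plates, limits differences in the assay but not in earlier handling. With morning and noon samples, an offset common to both would cancel in a within-day change, even at a single visit. Finally, leaving the decisive ANOVA term unnamed applies to every outcome and is not a fault of the saliva procedure.

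**Conclusion.** No change to the plan follows. The wording is loose and leaves out the intervention arm's collection day, place and storage, so a reader cannot confirm that handling was alike. That is a gap in description, not a demonstrated error. One plausible sense of the word collection reconciles the end sample, and the baseline sample conflicts only under an unstated assumption.

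The size of any bias is unknown and may be zero. The 15% and 45% figures hold only for assumed constant offsets of 0.25 and 0.5 SD. The term that would guard against a constant offset is already part of the planned two-way repeated ANOVA, and making it decisive would not help, and could hurt, if handling varied between visits.

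The study design section describes a trial already run, so sampling cannot be redone. Analysts with the collection records can state day, place and holding time by arm when they report cortisol. The point concerns one biomarker that the document does not make primary; the pain, quality-of-life and feasibility results do not depend on it.

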## **R21 Environmental Enrichment Study Protocol**

*Translation of the EE intervention:* The environmental enrichment (EE) paradigm was translated by a multidisciplinary team composed of investigators with expertise in psychology, physiology, neuroscience, integrative mind-body disciplines, gynecology, and translational research, together with consultants in HPA axis research and stress management, met during a period of one year to design an intervention to be tested in patients. A pilot randomized clinical trial was designed to test the efficacy of reducing painful symptoms and improving QoL as an adjuvant to standard care. The adaptation followed the ORBIT Model proposed by Czajkowski *et al.* (2015) to develop behavioral interventions for chronic diseases [refs]. This model guides the early pre-efficacy stages of the development of a behavioral intervention using a four-phase approach (F1: design, F2: preliminary efficacy, F3: efficacy, F4: effectiveness (F2 to be tested in the current proposal). Guided by the model, we translated a basic neurobehavioral finding (*stress control and EE reduces the growth of lesions in rats*) into a clinical question (*will an EE intervention be effective in reducing pain symptoms/inflammation and increasing QoL in women with endometriosis?*). First, we conducted a systematic literature review to select the approaches for the adapted EE intervention, using the PRISMA-P 2015 protocol and the PRISMA evaluation checklist. The process of translating the environmental enrichment (EE) paradigm has been described in detail in Nieves-Vázquez et al. (2022) [41].

**Recruitment**: After IRB approval (Protocol #1901004205R003) a recruitment campaign was conducted using social media (Facebook, Instagram, Twitter) of the Fundación Puertorriqueña de Pacientes con Endometriosis (ENDOPR), the only patient support association in Puerto Rico established in 2015. Recruitment for session one took place from September 2019 to December 2021 and then from May to June 2021. Recruitment for session two took place from August 2021 to February 2022. Patients interested in participating will be first screened for inclusion/exclusion criteria by our research coordinator and verbally consented to before being randomized into the intervention and control groups described below.

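### The efficacy analysis offers three unranked routes and names no ANOVA term as the test or the Tukey gate; an ANCOVA on baseline would be more precise at almost no cost

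*Combined protocol and SAP*

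**What the plan says.** Efficacy is a stated aim in two places. *Translation of the EE intervention* says "A pilot randomized clinical trial was designed to test the efficacy of reducing painful symptoms and improving QoL as an adjuvant to standard care", and *Study design of the pilot RCT* says "To evaluate the efficacy of a translated EE intervention for endometriosis patients, we conducted a RCT of parallel design", with 29 women in the EE arm and 27 on the wait list.

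*Statistical analysis* then gives three ways to examine outcomes:

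1. Univariate tests: "between-group differences in clinical-demographics variables and study outcomes were assessed using descriptive and univariate statistics". For continuous variables a Shapiro-Wilk check decides between a t-test and a Mann-Whitney test. The time point for the outcomes is not given.
2. Percent improvement: "Between group differences, as well as changes in the intervention group (from baseline) were evaluated for % improvement". Neither a definition nor a test is given.
3. Repeated-measures ANOVA: "Outcomes were evaluated using repeated two-way analysis of variance and assessed differences in intragroup (baseline vs. end of intervention) and intergroup (intervention vs. control".

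The follow-up step reads "If findings were significant, we used a Tukey post-hoc test". The significance level is 0.05. No route is called primary, the group-by-time interaction is not mentioned, and no model has a baseline covariate. The data for one exist, since "all subjects completed a set of validated surveys at baseline and end of the intervention", and both arms gave saliva at the same two stages. Only the EE arm was followed to 3 months.

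**The concern.** The routes estimate different things. The end-score test ignores baseline. The group main effect of the ANOVA averages in the baseline visit, when EE had not begun. The time effect and the within-EE percent improvement include any change that would have happened anyway. Of the ANOVA terms, only the interaction isolates the treatment effect, and it is the one not named.

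Two things are at stake. First, a trial at the preliminary-efficacy stage should hand on one clear effect estimate, and here several are available with no rule for choosing. A Tukey step opened by the time effect can show a significant change in EE and none in control when the arms do not differ. A shared change is plausible: women had to be symptomatic to enter, so regression to the mean is likely, and both arms could receive standard care.

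Second, precision is scarce with 56 women. Both the change score and the raw end score use the baseline less efficiently than regression on it.

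**Working it through.** **Inputs.** From the documents: n = 29 and 27, level 0.05, two visits common to both arms. There is no stated power or target effect to reproduce. Assumed: two-sided tests, a true effect d = 0.5 SD for illustration, equal SDs at both visits, normal data, no dropout, and a baseline-to-end correlation r of 0.3, 0.5 or 0.7.

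**Precision.** With two visits, the interaction F is the square of the change-score t. In units of SD² × (1/29 + 1/27), the variance of the treatment effect is:

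- end score only: 1
- interaction (change score): 2(1 − r)
- ANCOVA: (1 − r²) × [1 + 1/(56 − 4)] = (1 − r²) × 1.019
- group main effect, rescaled to the same effect: 2(1 + r)

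The noncentrality is d × √(29 × 27/56) / √variance = 0.5 × 3.739 / √variance. For the end score this is 1.87, giving 45% power on 54 df. ANCOVA uses 53 df.

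| | r = 0.3 | r = 0.5 | r = 0.7 |
|---|---|---|---|
| Variance: interaction | 1.40 | 1.00 | 0.60 |
| Variance: ANCOVA | 0.93 | 0.76 | 0.52 |
| Power: group main effect | 21% | 19% | 17% |
| Power: interaction | 34% | 45% | 66% |
| Power: end score | 45% | 45% | 45% |
| Power: ANCOVA | 48% | 56% | 72% |
| 80%-power effect: interaction | 0.90 SD | 0.76 SD | 0.59 SD |
| 80%-power effect: ANCOVA | 0.73 SD | 0.67 SD | 0.55 SD |

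The end-score test needs 0.76 SD for 80% power. Without the small-sample factor, ANCOVA power is 49/56/73%, and with 25 and 23 end scores (about 15% loss) it is 43/50/66%, against 30/40/59% for the interaction and 40% for the end score.

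ANCOVA beats the end score when (1 − r²) × 1.019 < 1, that is r above about 0.14. It beats the interaction when (1 + r) × 1.019 < 2, that is r below about 0.96. Outside that range it loses under 2% of variance.

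**Unranked routes** (simulation). With no treatment effect, the interaction and end-score tests disagree in about 8–9% of trials and at least one rejects in about 9%. Adding a between-group percent-improvement test (assumed to be per-participant percent change compared by ranks) makes that about 10%. At a true 0.5 SD the first two disagree in 30/34/40% of trials.

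**Tukey step** (simulation, no treatment effect). There are four cell means, q(0.95; 4, 54) = 3.749, so |t| must exceed 3.749/√2 = 2.651. The outcome counted is EE change significant, control change not; r is 0.5–0.6.

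| Shared shift | Any term opens Tukey | Only the interaction opens it |
|---|---|---|
| 0 | about 1% | about 0.5% |
| 0.15 SD | about 4% | 1.1–1.3% |
| 0.3–0.5 SD | 13–26% | 1.9–2.5% |

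With no shift the any-term gate still opens in about 14% of trials. Over r from 0.3 to 0.7, the range at 0.3–0.5 SD is 9–26%.

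**Non-normal outcomes** (simulation). ANCOVA type I error is 4.6–5.3% for a clipped 0–100 score, a 0–21 integer score with a floor, and log-normal data. For log-normal data (log SD 0.6) and a decrease of 0.5 SD on the log scale, power is 26/33/48% for the raw interaction, 42/48/62% for raw ANCOVA, 45/53/67% for rank ANCOVA and 47/56/72% for log ANCOVA. The plan's own Mann-Whitney test on the end score has 42–44% at every r.

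**The case against.** The univariate sentence opens with baseline equivalence and can be read as describing baseline comparisons only, and the percent-improvement sentence names no test. On that reading the ANOVA is the single inferential model, and the 9–10% figures largely fall away. The milder reading is possible, but the sentence does include study outcomes, and the ANOVA's missing test term and open Tukey gate remain either way.

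The interaction is already a valid test, so ANCOVA corrects no error. That stands: naming the interaction and ranking the routes would cure the ambiguity. ANCOVA is an efficiency gain on top. Its size depends on a correlation the documents do not give and is small in places: 45% to 48% over the end score at r = 0.3, and 66% to 72% over the interaction at r = 0.7.

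The Tukey risk needs a shared shift, an any-term gate and a reader who takes a within-arm contrast as efficacy. This also stands, and the figures are conditional on it.

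For log-normal data, raw ANCOVA gains nothing over Mann-Whitney at r = 0.3, and for an increase rather than a decrease its lead over the interaction nearly closes at r = 0.7 (about 62% against 59%). This supports settling the analysis scale outcome by outcome; log ANCOVA still leads.

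Finally, feasibility is also an aim, and the text is in the past tense, so new wording cannot restore pre-specification. Neither point removes the need to say which result carries the efficacy claim.

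**Conclusion.** The concern holds and should be fixed. The textual part is certain: no ranked route, no named interaction, no defined gate to Tukey, no baseline covariate. The false EE-only pattern is negligible (about 1%) without a shared change and becomes material at about 0.3 SD or more. ANCOVA's variance is about 0.66/0.76/0.87 of the interaction's at r = 0.3/0.5/0.7 (0.65/0.75/0.85 before the small-sample factor). These sizes rest on the assumed effect, correlation, shift, normality and complete data. ANCOVA's advantage over both alternatives holds for r from about 0.14 to 0.96. The figures are for one outcome; the many scales collected would add multiplicity.

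**What to change.** For each outcome measured at baseline and end in both arms, report one efficacy result: the between-arm difference at end with its 95% CI, from an ANCOVA of end score on arm and baseline score, in all randomised participants with an end score.

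- State the analysis scale for each outcome. Where residuals are clearly non-normal, add a rank-based or transformed ANCOVA (for example log cortisol) as the check, and say which result stands if the two differ. State which cortisol sampling time supplies the baseline and end values.
- Label univariate tests on outcomes and all percent-improvement comparisons as supportive or descriptive.
- If the ANOVA is kept instead, name the group-by-time interaction as its test and the only gate to Tukey.
- Base no efficacy claim on within-arm changes or on the EE-only 3-month data.
- If the analyses have already been run, label the ANCOVA as specified afterwards.

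The cost is SAP wording, re-run models and one degree of freedom per model (critical t 2.005 to 2.006). No new data are needed.

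### The Tukey step after the repeated-measures ANOVA has no stated family, gate or error term, and no single error term suits both its within-arm and its between-arm comparisons

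*Combined protocol and SAP*

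**What the plan says.** The Statistical analysis paragraph of the combined protocol and SAP gives the main method: "Outcomes were evaluated using repeated two-way analysis of variance and assessed differences in intragroup (baseline vs. end of intervention) and intergroup (intervention vs. control"). The next sentence adds: "If findings were significant, we used a Tukey post-hoc test". The threshold is "A p value of 0.05 or less was considered statistically significant", with no statement on sidedness.

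The study design paragraph gives 29 women in the intervention arm and 27 on the wait list, and says that "all subjects completed a set of validated surveys at baseline and end of the intervention". Each arm therefore supplies paired data at the two times that the ANOVA uses.

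The same analysis paragraph also lists a route to between-group differences that does not involve Tukey: "study outcomes were assessed using descriptive and univariate statistics, including T-test or Mann-Whitney test for continuous variables". It does not say which of the two routes decides efficacy.

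**The concern.** Tukey's method assumes independent means with one common error variance. In a 2 x 2 layout each ANOVA term has one degree of freedom and needs no post-hoc test, and with only two means Tukey is the ordinary t-test. The step therefore changes something only when it is run on the four arm-by-time means. Of the six pairs among them:

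- two are within-arm (the same women at baseline and end);
- two are between-arm at the same time;
- two cross arm and time, and answer no question.

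Within-arm and between-arm differences have different standard errors, so one error term cannot be right for both. At stake is how the between-arm p-values and intervals at end of intervention can be read. Depending on choices that the plan leaves open, they are too liberal or conservative.

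**Working it through.** The documents give no power or post-hoc error figure, so there is none to reproduce first.

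**Inputs from the documents.** n = 29 and 27; two times; alpha 0.05.

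**Assumptions.** Two-sided testing, normal data, equal variances (SD = 1), no dropout, baseline-to-end correlation r from 0.3 to 0.7, and the effect sizes named below.

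**Error terms.** With SD = 1, the within-subject mean square estimates 1 − r and the pooled mean square estimates 1. Tukey multiplies its mean square by (1/n_i + 1/n_j). The true variances are:

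- between arms at one time: 1/29 + 1/27 = 0.0715;
- change within an arm of size n: 2(1 − r)/n.

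The within-subject term thus fits the within-arm pairs but makes the between-arm standard error too small by a factor √(1 − r), which is 0.71 at r = 0.5. The pooled term fits the between-arm pairs but makes the within-arm standard error too large by 1/√(1 − r), which is 1.41 at r = 0.5.

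**Critical values.** q(0.95; 4, 54)/√2 = 2.651 (within-subject term); q(0.95; 4, 108)/√2 = 2.609 (pooled term); t(0.975; 54) = 2.005.

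**Error of the end-of-intervention between-arm comparison, within-subject term, no treatment effect.** Without a gate it is 2·P(t54 > 2.651·√(1 − r)). At r = 0.5, for example, this is 2·P(t54 > 1.874) = 6.6%. The gated columns come from 40,000 simulated trials per setting.

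| r | No gate (formula) | Any term opens, shared 0.5 SD change | Any term opens, complete null | Interaction must be significant, complete null |
|---|---|---|---|---|
| 0.3 | 3.1% | 3.0% | 2.3% | 0.9% |
| 0.4 | 4.5% | 4.6% | 3.1% | 1.0% |
| 0.5 | 6.6% | 6.7% | 4.0% | 1.1% |
| 0.6 | 9.9% | 9.6% | 5.1% | 1.2% |
| 0.7 | 15.2% | 15.5% | 6.5% | 1.6% |

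Error passes 5% only above about r = 0.43. The critical value 2.651 implies about 1% per comparison, 2·P(t54 > 2.651), so the ungated rate is above its intended level at every r shown. With the interaction gate, a shared time change leaves the error at about 1 to 1.6%.

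**Pooled term.** Between-arm error is 2·P(t108 > 2.609) = 1.0%. Power at an assumed 0.7 SD effect uses noncentrality 0.7/√0.0715 = 2.617:

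- pooled Tukey: about 51%;
- single end-of-intervention t-test: 73%;
- four-comparison Bonferroni t-test with the correct standard error (critical value 2.584): 52%;
- group-by-time contrast, noncentrality 0.7/√(2(1 − r)·0.0715): 73, 82 and 91% at r = 0.5, 0.6 and 0.7, and about 58 to 59% at r = 0.3.

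For a within-arm change of 0.5 SD at r = 0.5, simulated power is 17% for pooled Tukey against 74% for a paired t-test.

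**Check on the replacement.** In simulation the end-of-intervention t-test, the baseline-adjusted comparison and the group-by-time test all held 4.6 to 5.5% error. At an assumed 0.65 SD and r = 0.5, 0.6 and 0.7, power was 78, 84 and 91% for the baseline-adjusted comparison and 66, 77 and 87% for group-by-time.

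**The case against.** The strongest reply is that this is underspecification in a pilot, and that several ways of carrying out the sentence do no harm. Much of that stands. An interaction gate keeps the error low, a pooled term keeps the between-arm test valid, and software that uses contrast-specific standard errors would avoid the mismatch. The four-mean reading is not written down. The intervention arm also has a 3-month assessment, although the ANOVA sentence confines time to baseline and end.

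A reader might infer three stronger things that the documents do not support:

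- **That pairing costs the between-arm comparison its power.** It does not. With a pooled term that standard error fits, and the fall from 73% to 51% is nearly all multiplicity adjustment, because a correct-error Bonferroni test gives 52%.
- **That the two cross pairs cause the rise in critical value from 2.005 to 2.651.** Four comparisons alone already need 2.584. The step to 2.651 is about 0.07 of a rise of about 0.65.
- **That Tukey alone carries the efficacy reading.** The plan also lists t-tests or Mann-Whitney tests of study outcomes.

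What the reply does not remove is that the plan names none of the choices that would make the step safe. Its condition, a significant finding, is not limited to the interaction. A shared time change is plausible, since women entered while symptomatic and both arms could receive standard care.

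**Conclusion.** The point holds in conditional form. As written, the Tukey step cannot give correct within-arm and between-arm comparisons from one error term, and the plan does not say which term is used.

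The liberal case, about 3 to 15% error for r = 0.3 to 0.7, needs the within-subject term, a gate that any significant term opens, and a shared time change. It exceeds 5% only for r above about 0.43. It would be wrong to read 7 to 15% as the plan's error rate: the correlation, gate and error term are all absent from the documents, and other combinations give about 1 to 6%.

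The conservative case, the pooled term, is a valid test at about 1%, adjusted for six pairs of which two answer no question. Its within-arm standard errors are too large. The power figures rest on the assumed 0.7 SD effect. The matter should be corrected, but it does not by itself invalidate the trial's between-arm evidence.

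**What to change.** Delete the Tukey sentence. For each outcome, name one between-arm contrast before re-analysis, either group-by-time or the end score adjusted for baseline, and report it with its own standard error and 95% CI. State that this contrast, and not the separately listed t-test or Mann-Whitney test, is the efficacy comparison. Show within-arm changes as paired changes with confidence intervals, labelled descriptive, and do not test the two cross pairs.

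No new data are needed; the cost is SAP wording and re-analysis of existing data. The downsides are that adjustment across pairwise comparisons within an outcome is lost, and that some pairwise p-values disappear from the report.
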